Minimizing risk: Only trained personnel will perform phlebotomy. Patients who have symptomatic anaemia (Hb<8g/dl with symptoms attributable to anaemia) will not have more than 30ml of blood drawn. An SOP will be developed to guide

what key assays will be performed in such patients in order to maximize the investigations and assays that can be performed on this 30ml (those that impact on patient management will be prioritized).

Potential benefits: This study will not directly benefit participants. The study results will contribute to management and hopefully improve survival of patients with similar problems in the future. Many of the study investigations will be performed in real time (these are indicated in the table above) and results will be made available to the medical teams responsible. Participants will have an experienced and dedicated study team who will advise on their medical treatment during the first three months of tuberculosis treatment and during ART initiation (if applicable). People who choose not to participate in the study will still receive standard of care treatment for tuberculosis and HIV.

Informed consent process:

Process: A study team member will approach patients in the emergency room or medical wards. Every effort will be made to make the space as confidential as possible, i.e. draw curtains around the bed, look for a side room if patient is well enough to mobilize. The informed consent process will be delegated to the study nurse and the study counselor. The study medical officer will support the process. All study personnel will have Good Clinical Practice training and will follow these principles closely. The Principal Investigator will provide training of the study-specific informed consent process and monitor that informed consent is being taken that fulfills GCP requirements throughout the study. The informed consent document will be discussed with the patient in detail in their language of choice (Xhosa or English). The ICF's will be available in both languages. The patient will be given time to consider the study and time to discuss with their relatives if required. The patient will be given time to ask questions. At each follow up visit there will be opportunity to revisit any aspects of the study the participant may wish to.

Capacity to consent: If a potential participant appears confused, the study medical officer will assess the patient. If the patient is unable to give informed consent, and the participant is eligible for the study (i.e. known HIV infected and to be started on TB treatment during admission), the participant will be enrolled on the study. This will be discussed with relatives as outlined above. Once the patient regains cognitive ability to consent, the study will be discussed with them. If the patient is agreeable, they will sign the informed consent document. If they do not want to take part in the study, their samples and data will be destroyed. If the participant does not regain the ability to consent, specific permission will be sought from the UCT HREC to use that patient's data and sample for the study.

Comprehension of information: Patient's understanding will be tested with standard questions prior to signing the informed consent documents.

No information regarding the study will be withheld from participants.

The Informed Consent Form, Genetic Consent Form, Controls Consent Form and PK Study Consent Form will be translated into Xhosa once approved by the ethics committee.

Privacy and confidentiality:

Each participant will have a unique identifying study number and this will be recorded together with the patient's name and contact details in a study log. The study log will be kept in a locked cabinet in a limited-access office at Khayelitsha District Hospital. Only the study team will have access to these records. All clinical and laboratory data forms and samples will only be labelled with the patient's study ID number (apart from NHLS samples which will have the patient's name on them as outlined above). All data on the electronic database will be anonymised.

Reimbursement for participation:

Participants will be reimbursed for traveling expenses when they attend outpatient clinic visits (R100). Patients will be given a small food parcel on enrollment as a token of appreciation (total cost < R50). This will not be used as an incentive to persuade patients to be enrolled on the study, but rather be given after enrolment to say thank you for enrolling on the study. We are aware of the fact that we will be collecting a number of additional samples from these patients, which will take some time and effort from their side, especially at time of enrolment, and thus think a token of appreciation that also serves to provide additional nutrition is appropriate. Patients who also participate in the PK-studies on day 3 of TB treatment will be reimbursed transport money if they are attending an outpatient clinic as a control patient. This will be a minimum of R100 but may be more, depending on when recruitment for PK control patients start. Inpatients who are recruited in hospital will not receive a transport fee but will receive a toiletry hamper which contains basic toiletries that can be used during the patients hospital stay. If a patient is too ill to receive and use these items themselves every effort will be made to give this to an adult relative who spends time with this patient in hospital or the nurse who cares for this person at the time of the study.

Emergency care and insurance for research-related injuries:

The UCT Ethics Committee no faults insurance will cover all injuries incurred as a result of participation in the study. Emergency care will be provided by the clinical service at Khayelitsha District Hospital.

What happens at the end of the study?

Participants will be transferred to their appropriate primary care clinic with a referral letter at the end of 12 weeks. Results will be disseminated in local and international meetings and peer reviewed journals.

Study timelines:

Months 1-6	Months 7-42	Month 43-49	Months 50-60
Prepare SOPs, administration, recruit staff, ethical and PGWC permission			

	Recruitment and follow-up of clinical cohort and controls	
	Laboratory experiments	
		Analysis, interpretation and write-up of results

References:

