translocation of lipopolysaccharide (LPS) and other bacterial products contributing to immune activation and disease progression during chronic HIV infection [17, 18]. We hypothesise that in patients with advanced HIV and disseminated TB, intestinal immunity is more profoundly impaired (as both diseases affect the intestine and result in nutritional deficiency and intestinal hypoperfusion may complicate disseminated TB). High levels of LPS and bacterial DNA translocation resulting in immune activation may contribute to a sepsis syndrome associated with disseminated TB. Translocation of viable intestinal bacteria may result in fatal sepsis.

Work which has led up to this project:

We have published 2 studies that investigated the causes of clinical deterioration during TB treatment in hospitalized patients and outpatients respectively. In both, the most frequent causes for deterioration were AIDS-related opportunistic infections, TB-IRIS and bacterial infections (Appendix 1) [19, 20]. Nine patients in the hospital study were found to have extended-spectrum beta-lactamase producing Enterobacteriaceae infections (7 had a fatal outcome).

We also conducted a cohort study of inpatients with HIV-TB (n=113) during the first 3 months of ART to assess incidence and features of TB-IRIS, drug toxicities and opportunistic/bacterial infections at Brooklyn Chest TB Hospital. Nosocomial infections occurred in 16%: Enterobacteriaceae were isolated in 12/23.

A 2-year review of blood cultures at GF Jooste Hospital demonstrated 217 gram-negative (89 *E. coli*; 49 *Klebsiella* species) and 15 *Enterococcus* species (Appendix 2). These findings support the hypothesis of translocation of intestinal organisms. This is likely an underestimate of blood stream infections as insufficient blood cultures are routinely performed.

We supervised [name] at Madwaleni Hospital (Eastern Cape) who assessed predictors of 2-month mortality among admitted HIV-TB patients (Appendix 3). When data for the first 79 patients were analysed it was found that 35% died a median of 8 days (IQR= 6-20) after admission. Elevated lactate was independently associated with reduced survival (adjusted OR = 0.41 (95% CI = 0.24-0.71)).

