For paradoxical TB-IRIS, we performed a randomized placebo-controlled trial of prednisone treatment. A 4-week course of prednisone reduced morbidity and symptoms [21]. We have also published studies on the immunopathogenesis and diagnosis of TB-IRIS [22-25]. In the diagnostic study, among 100 patients presenting with suspected TB-IRIS, 7 were diagnosed with alternative opportunistic diseases and 9 with rifampicin-resistance [23].

Rationale and methods for each research question:

1a) Is fatal HIV-TB associated with a sepsis syndrome caused by *M. tuberculosis* itself resulting in major organ dysfunction and septic shock?

The hypothesis is that disseminated TB results in an inflammatory cascade in the blood causing sepsis syndrome, severe sepsis and septic shock [26-29]. Patients with mycobacteraemia, particularly with higher levels, would be more at risk for these complications and mortality. This hypothesis will be tested by correlating clinical and laboratory markers of sepsis with quantitative markers of *M.tuberculosis* load. All patients with positive bacterial cultures from blood or other sterile site or clinically diagnosed bacterial infection (e.g. pneumonia) will be excluded from this analysis.

Investigations: Patients will be assessed for clinical features of sepsis syndrome, severe sepsis and septic shock, defined using standard criteria [28]. Echocardiography will assess left ventricular function (dysfunction may occur with sepsis syndrome and contribute to shock). Laboratory investigations to assess sepsis syndrome: C-reactive protein (CRP) [30], procalcitonin [31, 32], full blood count, D-dimer [33], venous blood gas, lactate (Appendix 3), liver/renal function and glucose.

Investigations to assess *M.tuberculosis* load quantitatively:

- i) Mycobacterial blood culture (Days to positivity);
- ii) Quantitative urinary LAM Clearview TB ELISA;
- iii) Semi-quantitative urinary LAM Alere Lateral Flow Assay (Intensity measurement of bands serves as semi-quantitation);
- iv) Sputum Xpert MTB/RIF (Cycle threshold as relative quantitation) and culture (Days to positivity).

The individual quantitative measures of *M.tuberculosis* load will be correlated with markers of sepsis syndrome to assess association (univariate analysis and multiple linear regression), and comparisons will be made for all variables between fatal cases and survivors.

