To test the third hypothesis bacterial blood cultures will be performed on all patients on admission and at any clinical deterioration with fever or features of sepsis syndrome [28]. Sputum bacterial cultures will be performed on all with radiographic pulmonary infiltrates. Bacterial cultures will also be performed on other appropriate specimens (eg. urine, pus). The contribution of bacterial infection in general to clinical deterioration and deaths will thereby be ascertained. We will make assessment of the likely source of bacteraemia (eg. respiratory or urinary tract, intestinal) based on the organism and cultures from other clinical sites.

1c) Is fatal HIV-TB associated with cytomegalovirus (CMV) viraemia?

CMV viraemia has been associated with mortality in HIV-infected patients [43-47]. Amongst HIV-infected South African miners (mainly WHO stage 1 and 2) 10.9% had detectable CMV viraemia and this was associated with 3-fold higher mortality [48]. Undiagnosed organ disease (eg. pneumonitis) may contribute to mortality as suggested by post-mortem studies [13, 14]. Viraemia may also contribute to HIV disease progression [48]. It is also possible that CMV viraemia interferes with immune responses to other pathogens: CMV viral replication may directly damage infected immune cells through lysis and expansion of CMV-specific CD8 T-lymphocytes in peripheral blood may reduce the pool of naïve T-cells [49]. To address this hypothesis we will perform CMV viral load determination using quantitative PCR (Roche Cobas AmpliPrep/Cobas Taqman platform at Groote Schuur Hospital Virology Laboratory). We will also examine for features of CMV disease by:

- i) pan-optic fundoscopy;
- ii) gastro-intestinal tract biopsies in patients who have endoscopy and at post-mortem.

If a strong independent association between CMV viraemia and mortality is found we will propose and seek funding for an RCT of ganciclovir pre-emptive therapy or aciclovir prophylaxis, similar to practice in transplant recipients [50].

1d) Is fatal HIV-TB associated with immune activation-induced apoptosis and worsening immunosuppression?

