20 patients will be enrolled monthly. When potential enrollees exceed capacity on a day then recruitment will be randomised (using simple random allocation calculator) to avoid bias. This method of selecting participants to enroll will be described in an SOP. The study counselor or study nurse will administer the informed consent document with support from the study medical officer. The informed consent document makes it clear that patients will receive the same standard of care should they decline to take part in the study and that collection and testing of genetic material is optional. In addition, they will be specifically requested to consent to storage of samples for future research and informed that this is optional. After informed consent is obtained, the study team will follow up patients for 12 weeks initially as an inpatient then as an outpatient.

Research procedures and follow up (see table below):

Cumulative mortality at 12 weeks will be ascertained. Paradoxical TB-IRIS and other causes for clinical deterioration will be ascertained during the 12 weeks. Participants not on ART will initiate ART 2-8 weeks into TB treatment (2 weeks if $CD4 \leq 50/\mu l$).

Study assessments will be at 3 days (while in hospital) and subsequently every 3 days while patient remains hospitalized. The study team will review patients at any re-hospitalisation. The team will make telephonic contact at 4 weeks after enrolment and will do a clinical review of all participants at 12 weeks after enrolment. Additional study visits will be arranged in order to determine the cause of and assist with management of clinical deterioration if necessary. We will investigate for TB drug resistance and additional diagnoses (including serum cryptococcal antigen testing [80]). Patients with drug resistance or other diagnoses will be included in the study, with these findings recorded.

At discharge from hospital patients will be referred to their local TB clinic and for continuation of their TB treatment and their local ART clinic for initiation or continuation of ART. A referral letter will be written by the KDH staff or the research staff. If at any time point there is concern that patients are not on appropriate medication, the team will contact their local clinic. They will be asked to bring their medications and TB card to the clinical review visit.

Post-mortem examinations:

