Relatives will be approached for permission for post-mortem examinations. If unwilling to have a full post-mortem performed, permission will be sought to undertake post-mortem needle biopsies of lung, liver and spleen and bone marrow – an approach that yields important diagnostic information in HIV-infected patients [14, 81]. Tests performed on tissue samples will include: histological stains; Gram, fungal and ZN stains; immunohistochemical staining (CMV); and bacterial, TB and fungal cultures. This study will be performed in collaboration with [name] (Anatomical Pathology, UCT).

Study Outline of Activities:

	D0	D3	Wk2	Wk4	Wk8	Wk12	Deterioration
Informed consent	x						
Clinical Assessment	x	x				x	x
Samples Collected	x	* PK					#x
^Δ ART initiation CD4 ≤ 50			x				
^Δ ART initiation CD4 >50			x				

D: Day

Wk: Week

ART: Antiretroviral Therapy

PK: PK substudy in a subset of participants

* PK samples will be stored and run in batches retrospectively.

Samples taken at time of deterioration will not be research samples, but standard of care samples appropriate to investigate the patients' condition at that time point.

^Δ If patient is not on ART at time of recruitment

Detailed Study Procedures:

Study procedure	Time Point	Detail	Volume	Standard of care or research
Clinical Assessment	All time points	Examine for features of sepsis syndrome and TB IRIS	NA	Standard of care
	D0	* Pan ophthalmic fundoscopy for features of CMV retinitis	NA	Research
Echocardiography	D0 & Deterioration	* Assess left ventricular function	NA	Research
Blood tests	D0 & Deterioration	Chemistry: * Glucose	2 ml	Standard of care
		* Lactate		Research
		* D-dimer	5 ml	Research
		* Pro-calcitonin	1 ml	Research
		* Venous blood gas	1 ml	Research
		* Liver function tests	5 ml	Standard of care
		* Renal function tests		Standard of care
		* CRP		Standard of care
		Haematology: * Full blood count and differential	4 ml	Standard of care
		Plasma: LPS concentration	2 ml	Research
		Soluble CD14	1 ml	Research
		Intestinal fatty acid binding protein	1 ml	Research
		Microbiology: * Bacterial blood culture	8 ml	Standard of care
		* Mycobacterial blood culture	5 ml	Research
		* Serum cryptococcal antigen lateral flow assay	0.5 ml	Research
		Virology: CMV viral load	2 ml	Research
		* HIV viral load	2 ml	Research
		Immunology: PBMC	10 ml	Research
		* CD 4 count	2 ml	Standard of care
		Genetic: DNA	2 ml	Research
Luminex and ELISA for cytokines	Plasma from PBMC sample	Research		

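### The bacterial-infection exclusion in aim 1a has no time limit, so membership of that analysis can depend on later sepsis and death

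*Protocol*

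**What the plan says.** In the protocol's rationale for question 1a, the hypothesis is to be tested by "correlating clinical and laboratory markers of sepsis with quantitative markers of" *M. tuberculosis* load. The next sentence sets the exclusion: all "patients with positive bacterial cultures from blood or other sterile site or clinically diagnosed bacterial infection (e.g. pneumonia) will be excluded from this analysis". It gives neither an admission window nor the words at any time, and defines clinically diagnosed infection only by the example of pneumonia. The section ends by stating that "comparisons will be made for all variables between fatal cases and survivors".

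Three other places decide who can meet the exclusion:

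- Question 1b, third hypothesis: "bacterial blood cultures will be performed on all patients on admission and at any clinical deterioration with fever or features of sepsis syndrome".
- Post-mortem examinations: tissue tests include stains "and bacterial, TB and fungal cultures", where relatives agree.
- Research procedures and follow up: "Cumulative mortality at 12 weeks will be ascertained", so later infections have 12 weeks in which to appear.

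The footnote to the Study Outline of Activities says that samples at deterioration are standard-of-care rather than research samples. That makes the load and sepsis markers mainly D0 measurements, although the Detailed Study Procedures table also lists many of them at deterioration.

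**The concern.** Some exclusion is needed: sepsis from a bacterial co-infection is not sepsis from tuberculosis. The difficulty is timing. A patient with clean admission cultures who worsens in week 3 with fever is cultured again, and a positive result removes that patient's D0 load and sepsis markers from 1a. A patient who stays well is not re-cultured and cannot be removed in this way. A patient who dies and has a post-mortem has one more chance of exclusion that no survivor has.

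The protocol's own model makes this more than a technicality. Question 1d proposes that severe HIV-TB causes immunosuppression that favours bacterial infection, so a later infection may be a consequence of severe tuberculosis on the way to death. The background also reports that 7 of 9 patients with resistant Enterobacteriaceae infections died, which suggests that excluded patients will be enriched for deaths.

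The clinical limb of the rule has a further weakness. Procalcitonin, CRP and lactate are analysed in 1a and are also reported to the treating doctors in real time, so an undefined clinical diagnosis can be shaped by the variables under study.

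At stake is the fatal-versus-survivor comparison, which is the question in the title of 1a.

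**Working it through.** **1. The plan's own figure.** The sample-size figure closest to 1a is 242 in total for a two-fold difference in urinary LAM (1.62 v 3.24 ng/ml, SD 3.2, alpha 0.05 taken as two-sided, power 80%). With 15% mortality, r = 0.85/0.15 = 5.67 survivors per death.

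- Deaths needed = (1 + 1/r)(1.96 + 0.8416)² × SD²/difference² = 1.1765 × 7.849 × 10.24/2.6244 = 36.0.
- Total = 36.0 × 6.667 = 240.2, or 246.7 with deaths rounded up to 37. The stated 242 is reproduced.

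**2. Is power the problem?** The 600 for analysis comes from 660 less loss to follow-up and rifampicin resistance only, so the 1a exclusion is not in it. Start from 90 deaths and 510 survivors, with power = Φ(1.62/(3.2√(1/n₁ + 1/n₂)) − 1.96). Exclusion rates are assumed.

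| Excluded, deaths / survivors | Retained | Mortality in retained set | Power |
|---|---|---|---|
| none | 90 / 510 | 15.0% | 99.3% |
| 30% / 10% | 63 / 459 | 63/522 = 12.1% | 96.5% |
| 50% / 10% | 45 / 459 | 45/504 = 8.9% | 90.0% |

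Power for this contrast survives. The make-up of the analysis set does not.

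**3. When does unequal exclusion bias?** If deaths were removed at random with respect to load and sepsis, the mean load of the remaining deaths, and the odds ratio for a marker, would be unchanged; only apparent mortality would fall. Bias needs exclusion to depend on outcome and markers together. The protocol supplies that link, because sepsis features trigger the cultures.

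**4. Illustrative simulation.** Every input is assumed; overall mortality is 13–14%. Ranges cover a low (0.1) and a high (0.5) setting for clinical diagnosis of infection at deterioration. Load difference is deaths minus survivors in SD units.

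| Scenario and rule | Deaths / survivors excluded | Load difference | Load–sepsis correlation | Sepsis–death odds ratio |
|---|---|---|---|---|
| A. Load affects sepsis only: admission-only | 15% / 6% | 0.194 | 0.297 | 2.02 |
| A. unrestricted | 30–44% / 11–19% | 0.173–0.181 | 0.291–0.294 | 1.86–1.93 |
| A. unrestricted + post-mortem | 38–50% / 11–19% | 0.173–0.181 | 0.290–0.294 | 1.85–1.89 |
| B. Load also affects infection and deterioration: admission-only | 16% / 6% | 0.319 | 0.305 | 2.05 |
| B. unrestricted | 33–47% / 12–20% | 0.237–0.261 | 0.272–0.286 | 1.92–1.95 |
| B. unrestricted + post-mortem | 41–53% / 12–20% | 0.222–0.246 | 0.270–0.284 | 1.90–1.91 |
| C. Load affects infection and deterioration, not sepsis: admission-only | 15% / 6% | 0.136 | 0.011 | 1.99 |
| C. unrestricted | 31–45% / 12–20% | 0.076–0.092 | −0.019 to −0.006 | 1.86–1.94 |

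The load difference falls by 0.194 − 0.181 = 0.013 SD at least and 0.319 − 0.237 = 0.082 SD at most (0.319 − 0.222 = 0.097 with post-mortem cultures). The correlation falls by at most 0.305 − 0.272 = 0.033 (0.035 with post-mortem). With no true load–sepsis effect it stays between −0.02 and 0.01, so no spurious association appears.

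**5. Which population is the target?** In scenario B the true load difference was 0.306 among patients free of bacterial infection at admission and 0.226 among those who never acquired one. The admission-only rule (0.319) is close to the first. The unrestricted rule (0.237–0.261) lies between the two and nearer the second, a group that cannot be identified at enrolment.

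**The case against.** The best case for the plan has four parts.

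- **The window is unstated rather than wrong.** An admission-only reading is possible, the universal admission culture is not triggered by sepsis, and an analysis plan that is not shown may settle it. This stands in part: a reader might infer that the protocol says at any time, and it does not. But the rule is written for all such patients without limit, and that is its natural reading.
- **The analysis may not be confined to D0, and the exclusion may not cover the mortality comparison.** Several markers are also scheduled at deterioration, and the exclusion sentence follows the correlation, not the later fatal-versus-survivor comparison. Both points are open. The footnote on deterioration samples favours a mainly D0 analysis, and nothing exempts the mortality comparison.
- **The aim needs bacterial sepsis removed.** This stands fully. Dropping clinically diagnosed infection at D0 from the main exclusion would let culture-negative bacterial sepsis into an analysis of sepsis from tuberculosis.
- **The bias is modest and mostly towards no difference.** Under the assumed inputs, this is right.

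A reader might also extend the point to 1b and argue that unequal culturing inflates an association between ever being bacteraemic and death. The protocol specifies no such association. Its third hypothesis concerns translocation causing deterioration, for which cultures at deterioration are the relevant evidence.

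**Conclusion.** The point holds as a defect of an unlimited exclusion rule, not as an objection to excluding. Followed literally, the rule lets membership of the 1a set depend on later sepsis and on death. That can bias the fatal-versus-survivor comparison, probably towards no difference, and has less effect on the load–sepsis correlation.

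Size and direction cannot be fixed from the document. The shifts shown rest wholly on assumed rates of infection, detection and death, and they count as bias only if the target is patients free of bacterial infection at admission.

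A reader might apply the 16% nosocomial infection rate in the background to 600 and forecast 96 lost patients. The document does not support that: the rate comes from 113 inpatients at a different TB hospital during the first 3 months of ART, and the overlap with the 1a rule is unknown.

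**What to change.** Reword the 1a exclusion as follows:

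- **Main analysis:** exclude only bacterial infection present at admission, meaning a positive admission (D0) culture, or clinically diagnosed infection at D0 by a pre-specified definition judged blind to outcome. Keep patients whose bacterial infection is found only later or at post-mortem. State that the rule governs both the load–sepsis correlation and the fatal-versus-survivor comparison.
- **Sensitivity analyses:** (a) the unrestricted exclusion; (b) exclusion on D0 culture only; (c) all patients kept.
- **Reporting:** numbers and reasons for exclusion by vital status.

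The cost is wording and a blinded review of D0 records; no new samples or visits are needed. The small downside is that some retained patients will later acquire a bacterial infection, which sensitivity analysis (a) addresses.
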